3.3 Power and Sample Size (as was written in the grant)

Power Analyses and Sample Size Calculations for Delirium (Aim 1). Based on data collected during our BRAIN-ICU Study, we anticipate that patients in the control (placebo) group in MIND-USA will have a mean ± SD of 6.8±5.2 delirium/coma-free days during the 14-day Treatment Period. At a 2-sided significance level of 2.50%, after Bonferroni adjustment for 2 pairwise comparisons (each active treatment will be compared to placebo), a trial of 187 patients per treatment group (total N=561) will have 92% analytical power to detect a 2-day improvement in delirium/coma-free days. Importantly, this sample size will also provide 80% power to detect a 2.5-day improvement in DCFDs within 4 subgroups expected to be ~45% (N=252) of the study population: severe sepsis, age ≥65 years, high illness severity (APACHE II ≥25), and medical vs. surgical patients. We will also conduct a hypothesis-generating subgroup analysis for patients enrolled with preexisting cognitive impairment (~25% of study population, N=140).

Power Analyses for Mortality and ICU LOS (Aims 2 and 3). Assuming 40% one-year mortality in the control (placebo) group, this study will have 80% power to detect a 13% absolute difference in one-year mortality at a 2-sided significance level of 1.67% (if control mortality is 50%, study has 80% power to detect 14% difference). For ICU length of stay (LOS), this study will have 80% power to detect a 2-day (24%) difference at a 2-sided significance level of 1.67% assuming an 8.2±7.6 day ICU LOS in controls.

Timing of Final Analysis

In-Hospital Database Cleaning & Lock Procedures

MIND-USA uses the REDCap electronic data capture platform for data collection. Upon completion of the in-hospital portion of the MIND-USA study, the following procedures will be followed and documented within the Database Cleaning & Lock SOP:

- 1. VCC will work with site coordinators to address all data issues revealed by ongoing data cleaning. This process will continue until all issues have been addressed.
- Upon completion of in-hospital data cleaning, the REDCap database MIND-USA Study: Exclusion Log will be locked in the following way:
 - a. Initially all users with current "view and edit" user privileges will be moved to "read only" user privileges.
 - b. After the window closes for sites to export their data the database will be permanently moved to inactive status (meaning that no data can be changed).

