- 3. Upon completion of in-hospital data cleaning, the REDCap database **MIND-USA Study: In-Hospital Database** will be locked in the following way:
 - a. Initially all study site personnel will be restricted to "read-only" user access for the entire database. VCC Project Managers and the Follow-Up Team will be restricted to read-only access for all fields except those needed for patient contact, reconsenting, DNA permissions, notes to file and event reporting, and tracking dates of death and study withdrawal. All fields not needed by these teams will be restricted to read only by use of the @readonly action tags. The follow-up team will continue to be blinded (via restricted access) to all information about the hospital course, as has been the case throughout the study.

	VCC Project Managers	Follow-Up Team
Dates Tracking Form - all variables made read-only (using action tag @readonly) to all users except variables pertaining to consenting, death and study withdrawal	View and Edit	View and Edit
Contact Form - all fields	Read Only	View and Edit
NTF - all fields	View and Edit	View and Edit
Adverse Events - all fields	View and Edit	View and Edit
DNA Log - all fields	View and Edit	No Access
All other forms/fields	Read Only	No Access

- b. During the remaining Follow-Up period, the sites will be given a window for downloading their data for local storage.
- c. Once 12-month follow-up is completed, we will conduct final data cleans on the updated information and then permanently move the entire database to inactive status, meaning that no data can be changed unless serious errors are noted.

A log of all steps in this process will be maintained in the Database Cleaning & Lock SOP.

4. Statistical Principles

Statistical analysis will be conducted in accordance to the plan outlined in this SAP. Statistical analysis will abide by these general statistical principles below.

Confidence Intervals and P-Values

Level of statistical significance will be set at 5% (with multiple comparisons adjustments for the primary outcome, as noted below). All tests will be two-sided. 95% confidence intervals will be reported along with all effect estimates. Presentation of results will emphasize clinical significance, effect sizes and confidence intervals, over statistical significance.

Modeling Principles

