Whenever possible (based on variable distribution), we will not assume linear associations between covariates and outcomes; rather, nonlinear associations between continuous variables and outcomes will be permitted by inclusion of restricted cubic splines with 3 knots. To account for correlation among patients within a given site, we will adjust standard errors using Huber-White sandwich estimation.

Multiple Comparisons

For the primary outcome (DCFDs), multiple comparisons will be conducted at a 2.5% level if the overall test of association is significant at a 5% level. Regarding the analyses of all *a priori*-defined secondary outcomes described herein, no adjustments will be made for multiple comparisons, in keeping with authoritative recommendations on this topic and standard practice when analyzing multiple, prospectively defined outcomes in a clinical trial. As described in our proposal, each comparison made will be hypothesis-driven and based upon biological plausibility rather than hypothesis-generating in nature.

Missing Data

Individual Variables

Missing data for individual variables will be imputed using clinical imputation rules when appropriate; details on these rules are noted in the Definitions and Derived Variables section. This section also describes the imputation process for summary variables for mental status (eg, days alive and free of delirium and coma), which may involve *partially* missing data.

Missingness when Modeling

In adjusted analyses, model-based multiple imputation strategies will be used (using R's mice library) if >5% of any covariates are missing. In all cases, decisions and processes will be documented both in data management and analysis code and in statistical reports.

Adherence to the Intervention and Protocol Noncompliance

Definition & assessment of adherence to the intervention

All analysis will be conducted based on the intention to treat principle. Subjects will be considered to have the treatment they were randomized to regardless of withdrawal from treatment or extent of exposure.

Presentation of adherence to intervention

We will describe, within each treatment group, the following:

- Patient level:
 - How many randomized patients received >=1 dose of study treatment
 - Days each randomized patient received study treatment
 - Doses of study treatment each randomized patient received, along with average daily dose

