All in-hospital outcomes will be analyzed using both univariate methods and multivariable regression, adjusting for covariates noted below. Though patient characteristics should theoretically be balanced between treatment groups due to randomization, adjustment increases our power and precision. Though we will perform both types of analyses for each outcome, adjusted analyses will be considered the primary analysis.

Unadjusted Analyses

In-Hospital Continuous Outcomes

We will analyze continuous outcomes (delirium/coma-free days [PO]; delirium duration [total, SO2; hyperactive and hypoactive delirium separately; coma duration; mean CV SOFA and lowest mean arterial pressure]) using the Kruskal-Wallis test. These outcomes are typically not normally distributed; therefore, the assumptions for a parametric ANOVA would be violated, and results would be unreliable. The nonparametric Kruskal-Wallis test does not assume that the outcome has a normal distribution, and thus provides more power and reliability in the case of a non-normal distribution.

If the unadjusted test for the primary outcome (DCFDs) only is statistically significant, we will use Dunn's test for pairwise differences between treatment groups, using a Bonferroni correction for multiple comparisons at a 2.5% alpha level.

Time to Event Outcomes

We will describe and test for differences in time to death (**SO1**) using Kaplan-Meier curves and the log-rank test, respectively. ICU and hospital discharge, liberation from mechanical ventilation, and ICU readmission all have a competing risk of death (**SO3**, **SO4**, **SO5**, and **SO6**, respectively). (For ICU readmission and liberation from mechanical ventilation, hospital discharge without experiencing the outcome will be treated as an additional competing risk.) Therefore, we will describe the cumulative incidences of both the outcome of interest and each competing risk, along with a modified chi-squared test for the difference between groups in the subdistribution of interest (Gray 1988). Patients who withdrew in the hospital with no discharge or death information available are censored at the time of withdrawal; we censor at x.01 days anyone who has experienced neither death nor the outcome of interest by x days (where x is the end of the time frame specified above for each outcome). We will detail how many and when patients were censored for each analysis.

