"Time 0" will be the time of randomization for each of these outcomes, with the exception of ICU readmission; for this outcome, "time 0" will be the time of the first ICU discharge, and only patients who survived their first ICU admission will be included.

Long-Term Outcomes

We will use multivariable regression to analyze the relationship between treatment group and scores measuring long-term neuropsychological, quality of life, and PTSD outcomes as outlined in the Outcomes section above. Depending on the distribution of each outcome, we will use linear regression, negative binomial regression, or proportional odds logistic regression, as appropriate. These models will not include covariates other than treatment.

For each outcome, we will have separate models for 3- and 12-month scores. At each time point, we include all patients with available outcome data, using inverse probability weighting to account for patient death and attrition. To decrease reliance on a few highly influential observations, we will truncate weights at the top 1 percentile.

As a sensitivity analysis, we will also define long-term outcomes using the unadjusted composite endpoint approach (reference: Lachin) to deal with outcomes truncated due to death or loss to follow up. The composite endpoint will be defined as:

- If the patient dies prior to assessment: days between randomization and death
- If the patient survives and is successfully assessed: days between randomization and planned assessment (constant) + assessment score

For example, if we are analyzing a 3-month outcome, the constant would be 90. Differences between the composite end point distribution amongst groups will be assessed using the Kruskal-Wallis test.

Adjusted Analyses

We will adjust all coefficient variances using Huber-White sandwich estimation, clustered by study site. This will help account for unmeasured variability and correlation among patients within a given site.

In-Hospital Continuous Outcomes

We will use proportional odds logistic regression for continuous outcomes (delirium/coma-free days; delirium duration [any, hyperactive, and hypoactive]; coma duration; mean CV SOFA and lowest mean arterial pressure); this method assumes an ordinal outcome but does not assume that it follows a specific statistical distribution.

If the overall test for treatment vs our primary outcome (DCFDs) is significant at the 5% level, we will report individual treatment tests vs placebo at the 2.5% level.

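### For delirium/coma-free days the SAP applies a 5% global gate and then a 2.5% Bonferroni level, but reports 95% intervals: valid and conservative, yet it gives up some power and lets intervals and tests disagree.

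*SAP*

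**What the plan says.** The SAP sets the rule for DCFDs in section 4, Multiple Comparisons: "multiple comparisons will be conducted at a 2.5% level if the overall test of association is significant at a 5% level". Section 7 repeats it for the adjusted proportional odds model: after a significant overall test, "we will report individual treatment tests vs placebo at the 2.5% level". Section 7 also states that "adjusted analyses will be considered the primary analysis", so this is the rule that decides the trial.

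The unadjusted analysis uses a Kruskal-Wallis test followed by Dunn's test, "using a Bonferroni correction for multiple comparisons at a 2.5% alpha level".

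The 2.5% comes from the sample-size calculation in SAP 3.3 and Protocol 11.1: "At a 2-sided significance level of 2.50%, after Bonferroni adjustment for 2 pairwise comparisons". That calculation mentions no global gate.

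On intervals, SAP section 4 (Confidence Intervals and P-Values) says "95% confidence intervals will be reported along with all effect estimates". The neighbouring sentence on significance makes an exception for the primary outcome; the interval sentence makes none. The paragraph ends: "Presentation of results will emphasize clinical significance, effect sizes and confidence intervals, over statistical significance".

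**The concern.** Two corrections for the same multiplicity are stacked. In a three-arm trial, if both drug-versus-placebo nulls are true then all three arms are equal. The 5% global test covers that case. When only one of the two nulls is true there is a single true null to protect, and a 5% test protects it. The gate followed by 5% tests is therefore a closed test for these two contrasts, and a further halving is not needed for 5% family-wise control.

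Two things are at stake. One is power, which matters most for smaller effects and for showing that both drugs work. The other is consistency: a contrast judged at 2.5% is displayed with an interval that corresponds to a 5% test, in a plan that tells readers to give intervals more weight than significance. A primary contrast with p = 0.03 would be not significant, beside an interval that excludes no effect.

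**Working it through.** **Inputs.** SAP 3.3: 187 patients per arm, SD 5.2 days, 2-day effect, two-sided 2.5%, stated power 92%. SAP section 4: global test at 5%, then pairwise tests at 2.5%, with 95% intervals. The 1-day and 1.5-day effects are added here to show how the cost changes; they are not planning values.

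**Reproducing the stated power (no gate).** SE of a difference = 5.2 × √(2/187) = 0.538 days. The ratio 2/0.538 is 3.72, and the two-sided 2.5% critical value is 2.241. Power = Φ(3.72 − 2.241) = Φ(1.48) = 93.0%. A noncentral t gives 92.9%. Assuming a rank-test efficiency of 0.955 gives 91.8%. The plan's 92% is reproduced.

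**Gated rules.** These come from 2,000,000 draws per scenario of three normal arm means: a 2-df chi-square global test at 5%, then z tests against placebo. This approximates the rank tests and the proportional odds model.

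| Scenario | SAP rule (gate, then 2.5%) | Gate, then 5% | Difference |
|---|---|---|---|
| Power, one drug, 2 days | 92.8% | 95.3% | 2.5 points |
| Power, one drug, 1.5 days | 69.6% | 75.3% | 5.7 points |
| Power, one drug, 1 day | 32.9% | 37.7% | 4.8 points |
| Both declared, both 2 days | 88.0% | 92.8% | 4.8 points |
| Both declared, both 1.5 days | 56.6% | 67.6% | 11.0 points |
| Family-wise error, neither works | 3.6% | 4.2% | |
| Family-wise error, one null, other strong | 2.5% | 5.0% | |

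Per-drug power for a 2-day effect is the same to within 0.1 point whether the other drug has no effect or also gains 2 days. If the other drug gains 1 day, the gate passes less often and the SAP rule gives 91.5% for the 2-day drug. Protocol 11.5 gives a final global threshold of 0.0498, where the SAP has 5%. Using 0.0498 moves power under the SAP rule by at most 0.03 points.

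**Interval against test.** The 95% half-width is 1.960 × 0.538 = 1.05 days. The 97.5% half-width is 2.241 × 0.538 = 1.21 days. An observed difference between the two has a 95% interval excluding zero but fails the 2.5% test.

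The table gives the chance that a drug's interval excludes zero while no claim is made for that drug. It counts failures of the gate as well as failures of the pairwise test.

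| True effect (other drug null) | SAP as written | 2.5% with 97.5% intervals | 5% with 95% intervals |
|---|---|---|---|
| 0 | 3.0% | 0.5% | 2.5% |
| 1 day | 13.1% | 2.2% | 8.3% |
| 1.5 days | 10.0% | 1.2% | 4.3% |
| 2 days | 3.2% | 0.2% | 0.8% |

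The mismatch in the last two columns comes entirely from the gate: the interval excludes zero but the global test is not significant.

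**Dunn sentence.** If someone corrected over three pairs and then judged at 2.5%, the raw level would be 0.025/3 = 0.83%. Power at 2 days would then be 86.0%.

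**The case against.** The strongest reply is that nothing promised is lost. The sample size was set at 2.5%, the gated rule still delivers the stated power, and a prespecified conservative rule is the sponsor's choice. That stands. A reader might infer that the double correction leaves the trial underpowered or distorts its error rate upwards. The documents support neither: power at the planned effect is about 92 to 93%, and under nominal tests the rule errs on the safe side.

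A second reply is that 5% tests after the gate are safe only if each test holds its level. The primary model uses a Huber-White variance clustered by site, and the SAP describes no small-sample correction. The documents give no site count. With 12 to 30 sites assumed, a rough simulation of a linear stand-in with an uncorrected clustered variance gave these error rates:

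- Neither drug effective: family-wise error of about 6 to 10% with 5% tests after the gate, and about 5 to 9% under the SAP rule.
- One drug strongly effective: false claims for the null drug of about 7 to 9%, and about 4 to 6% under the SAP rule.

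So the 2.5% step can act as a buffer, and it would be wrong to say it can never help. But this is a variance problem that should be solved as such. In that simulation the SAP rule also exceeds 5% at most assumed site counts when neither drug works.

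Third, moving to 5% does not make intervals and tests agree fully. That is correct: the gate leaves 4.3% mismatch at 1.5 days and 8.3% at 1 day.

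Fourth, the Dunn sentence might be read as a third correction that brings power down to 86%. That is only a possible misreading. SAP 3.3 defines 2.5% as the level already corrected for two comparisons, and the unadjusted analysis is not primary.

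**Conclusion.** The point holds as an inefficiency and an inconsistency, not as an error in validity. The Bonferroni step on top of the gate is not needed for nominal 5% family-wise control of two placebo contrasts. Against the less strict closed test it costs 2.5 points of per-drug power at the planned effect. The cost reaches 11 points for declaring both drugs at 1.5 days.

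The interval mismatch is the more practical defect. It does not depend on accepting the closed-test argument, and the SAP's own emphasis on intervals makes it visible.

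The figures assume normal arm means, a common SD of 5.2, 187 analysed per arm and tests that hold their nominal level.

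**What to change.** Amend the SAP before unblinding, choosing one of these:

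- **(a)** Keep 2.5% per drug and report 97.5% intervals for the two primary drug-versus-placebo contrasts. This keeps the prespecified level and cuts the mismatch at 1.5 days from about 10% to 1.2%.
- **(b)** After a significant global test, test each drug against placebo at 5% as a closed test, with 95% intervals. This recovers the power shown above. It also loosens the 2.5% level in Protocol 11.1, so it needs a documented justification and assurance that the site-clustered variance holds its nominal level.

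Under either option, state that no efficacy claim is made from an interval when the global test is not significant.

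In section 7, Unadjusted Analyses, state that Dunn's test covers only the two placebo contrasts, with raw p-values compared with the chosen level.

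No new data are needed. Option (a) is a wording change. Option (b) is a change to a prespecified decision threshold and should be recorded as one.

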 - Whether study treatment was ever held or permanently discontinued, and reasons for hold/discontinuation
- Dose level:
 - Proportion of opportunities to receive study treatment which were given, temporarily held, or permanently discontinued
 - Amount (mL) of each dose given
 - Whether dose amount was maintained, increased, or decreased
 - Reasons for hold or discontinuation

Definition and description of protocol noncompliance

Any noncompliance that increased safety risk to the patient was considered protocol noncompliance. These events will be captured for a variety of causes considered related to patient safety and will be described in the final study report, broken down according to a simple categorization scheme followed prospectively during the conduct of the MIND-USA investigation.

Analysis Populations

All analysis will be conducted on the randomized, intent-to-treat population. We will also compare demographic and admission characteristics of patients who were enrolled but not randomized to those who were randomized.

Analysis for all **in-hospital** outcomes will include all randomized patients in an intent-to-treat manner, with the following exceptions:

- Liberation from mechanical ventilation will include only patients who were on mechanical ventilation (invasive or noninvasive) at or within 24 hours following the time of randomization.
- 2. ICU readmission will include only patients who survived and remained in the study with access to medical data throughout their first ICU admission.

Analysis for **long-term** outcomes will include all patients who survive and remain in the study at the specified time point (3 or 12 months after randomization), and who have data for the outcome in question. We will describe the general cohort of patients who are included in any long-term outcome models at each time point.

5. Trial Population

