The study inclusion and exclusion criteria can be obtained from clinicaltrials.gov. Patient flow information as recommended by CONSORT guidelines will be presented for both enrolled and randomized patients, including screening, exclusions, refusal of consent, enrollment, randomization, withdrawals, and hospital discharge status. We will describe, by treatment group and overall, baseline characteristics of randomized patients including demographics (age, race, ethnicity, gender, insurance status, education, BMI); baseline clinical status (comorbidities, home antipsychotic use, frailty, disability, cognition); and ICU admission characteristics (admission reason, severity of illness).

6. Statistical Analysis

Outcome Definitions

Primary outcome (PO)

The primary outcome is delirium/coma-free days (DCFDs) over a 14-day study period, defined as the number of days during the 14-day intervention period (beginning on the day of randomization) that the patient was alive and experienced neither delirium nor coma.

Secondary outcomes (SO)

Time frames, as noted in parentheses, all begin on the day of randomization to study treatment, with the exception of ICU readmission.

SO1. Survival

Description: Time to death

o Time frame: 30 days, 90 days, 1 year

SO2. Delirium duration

o Description: Duration of delirium during the intervention period

o Time frame: 14 days

SO3. Time to final ICU discharge

- Description: Days from randomization to final, successful ICU discharge, where "successful" indicates that discharge was followed by at least 48 hours alive.
 "ICU discharge" is represented by readiness for ICU discharge indicated by a physician order for transfer to a lower level of care even if a bed availability problems prevent actual discharge from the ICU.
- o Time frame: 90 days

SO4. Time to hospital discharge

- Description: Days from randomization to successful hospital discharge, where "successful" indicates that discharge was followed by at least 48 hours alive.
- o Time frame: 90 days

SO5. Time to liberation from mechanical ventilation

- Description: Days from randomization to successful liberation from mechanical ventilation, where "successful" indicates that liberation was followed by at least 48 hours alive and without reinitiation of invasive or noninvasive ventilation.
- o Time frame: 30 days

SO6. Time to ICU readmission

- Description: Days from first ICU discharge to next ICU readmission within the index hospitalization.

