Patients could have multiple assessments on a given study day. On a given day, a patient was considered delirious if any assessment was considered delirious; comatose if no assessments met criteria for delirium and at least one was considered comatose; and normal if no assessments met criteria for delirium or coma, and at least one was considered normal.

Handling Missing Data

Prior to unblinding, the data shows that among all consented patients, 401 (4%) in-hospital patient-days have insufficient information to determine mental status (due to missing data or study withdrawal). Among randomized patients during the intervention period, 251 (4%) of patient-days have missing mental status, again due either to missing data or study withdrawal. Mental status can change quickly; therefore, simple imputation methods like last observation carried forward could be inaccurate. Since we have strong covariate data, we performed single imputation using polytomous logistic regression, including the following variables as covariates in the imputation.

- Baseline: age at consent; gender; BMI; education; level of proficiency in English; insurance; home antipsychotic use; Charlson comorbidities index; CSHA Clinical Frailty Score; APACHE II Acute Physiology Score
- Daily:
 - Medications (clonazepam, dexmedetomidine, propofol, remifentanil, antipsychotics, benzodiazepines, opioids [IV and PO], antibiotics, anxiolytics, statins)
 - Variables indicating severity of illness (CV SOFA, creatinine, urine output, platelets, lowest recorded RASS, Glasgow Coma Scale, P/F ratio, S/F ratio, bilirubin)
 - Any mental status data available the day of, the day before, and the day after the missing day

All summary variables (delirium/coma-free days, delirium duration, and coma duration) are presented using imputed mental status.

9. Software Details

R version 3.4.4 (2018-03-15) or above will be used for all analyses. Versions of specific packages used for analysis will be noted in the analysis report. The checkpoint.package will be used to preserve R package versions throughout the manuscript submission and review process.

10. References

- 2. R. Gray. A class of k-sample tests for comparing the cumulative incidence of a competing risk. Ann Stat, 16:1141-1154, 1988.

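### Delirium duration (SO2) is tested as a raw day count with no rule for death or coma, so early death or deeper coma can pass for shorter delirium

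*SAP*

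**What the plan says.** - **Definition.** SAP section 6 (Outcome Definitions) describes SO2 as "Duration of delirium during the intervention period", time frame 14 days, and adds nothing about death or coma.
- **Who is analysed.** SAP section 4 (Analysis Populations) says in-hospital "outcomes will include all randomized patients in an intent-to-treat manner, with the following exceptions". The two exceptions are ventilator liberation and ICU readmission, so early deaths stay in SO2.
- **Tests.** SAP section 7 analyses "delirium duration [total, SO2; hyperactive and hypoactive delirium separately; coma duration; mean CV SOFA and lowest mean arterial pressure]) using the Kruskal-Wallis test". For the adjusted version, which the SAP treats as primary, it says "We will use proportional odds logistic regression for continuous outcomes". The covariates are all fixed at or before randomization.
- **Daily state.** SAP section 8 (Mental Status) has three states: delirious, comatose and normal. A day is "comatose if no assessments met criteria for delirium and at least one was considered comatose". There is no state for death.
- **Multiplicity.** SAP section 4 sets 5% two-sided, with no adjustment across secondary outcomes.

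Elsewhere the SAP does deal with death. DCFDs count days "that the patient was alive and experienced neither delirium nor coma". Section 7 notes that "ICU and hospital discharge, liberation from mechanical ventilation, and ICU readmission all have a competing risk of death" and uses competing-risk methods for them. For long-term outcomes, a sensitivity analysis scores deaths below every survivor: "If the patient dies prior to assessment: days between randomization and death".

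**The concern.** Fewer delirium days will be read as better. Under these rules a patient can accumulate fewer of them by recovering, by dying, or by passing from delirium into coma. The tests cannot tell the three apart, and baseline covariates cannot remove an effect that arises after randomization.

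The protocol gives reason to care about both harms. Section 2.3 reports a mortality signal with antipsychotics in other populations, and section 2.4 lists oversedation among the adverse effects of haloperidol reported in a survey. The label adds risk: the protocol's Specific Aims and section 4.2.1 use delirium duration as a name for the primary outcome, although SO2 is not in the protocol's list of secondary endpoints. A nominally significant SO2 could therefore be taken as an answer to the main question.

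**Working it through.** **1. The plan's own figure.** The documents give no power figure for SO2. For DCFDs they state 92% power (187 per arm, 2 days, SD 5.2, two-sided 2.5%). Check: 2 / (5.2 × √(2/187)) = 3.719; 3.719 − 2.241 = 1.478; power = Φ(1.478) = 93.0%. With rank-test efficiency 0.955: 3.719 × √0.955 − 2.241 = 1.393, or 91.8%. The stated figure reproduces.

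**2. Direction, by hand.** Take three patients, all delirious at randomization.
- A: delirious on days 1-2, dead from day 3. SO2 = 2, DCFDs = 0.
- B: delirious on days 1-6, then clear. SO2 = 6, DCFDs = 14 − 6 = 8.
- C: delirious on days 1-2, comatose on days 3-6, then clear. SO2 = 2, DCFDs = 14 − 2 − 4 = 8.

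SO2 ranks A and C equal, and both ahead of B. DCFDs put A last and B and C level. No rate assumption is needed for this.

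**3. Consistency with the SAP's counts.** Section 8 reports 251 missing mental-status days as 4% of patient-days in randomized patients. That implies 251/0.04 = 6,275 days, or 5,578 to 7,171 allowing for rounding (4.5% to 3.5%). A full window for 561 patients would be 561 × 14 = 7,854. If at least 561 were randomized, some days (after death, discharge or both) lie outside that base. This fits post-death days adding no delirium days, but does not prove it.

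**4. Size, by simulation.** From the documents: 187 per arm, three arms, 14 days, Kruskal-Wallis at 5%. Assumed: everyone starts delirious; daily death risk 1.5% in delirium, 3% in coma, 0.3% when clear; delirium to coma 6% a day; coma to delirium 30%; relapse 4%; recovery varying between patients as Beta(0.62, 1.7). The chance of clearing delirium, given neither death nor coma that day, is the same in all arms. Both drug arms share the harm. There were 2,000 trials per row. Placebo DCFDs come out at 6.3 ± 5.3 (plan: 6.8 ± 5.2). Favourable means p < 0.05 with lower ranks on drug.

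| Scenario | 14-day deaths | Delirium days | DCFDs | SO2 favourable | Deaths ranked worst |
|---|---|---|---|---|---|
| No effect | 13.4% | 5.82 | 6.29 | 2.3% | 2.4% |
| Death hazard ×1.5 | 19.1% | 5.61 | 6.10 | 7.2% | 0.6% |
| Death hazard ×2 | 24.6% | 5.39 | 5.93 | 13.9% | 0.0% |
| Death hazard ×3 | 34.0% | 5.02 | 5.61 | 39.2% | 0.0% |
| Delirium to coma ×2 | 15.0% | 5.43 | 5.78 | 6.6% | 2.6% |
| Delirium to coma ×3 | 16.4% | 5.11 | 5.30 | 17.7% | 3.4% |
| Death ×2 and coma ×2 | 27.4% | 5.02 | 5.42 | 30.7% | 0.1% |

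In every harm row, delirium days and DCFDs both fall, so SO2 points the wrong way. With deaths ranked worst, the test signals harm in 30.4% of trials (hazard ×2) and 84.7% (×3). For the tripled coma rate it signals harm in only 1.8%, whereas DCFDs do so in 41.4%.

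**5. Sensitivity to the assumed rates.** Other four-state chains, with 12% to 15% 14-day mortality, gave:
- doubled death hazard: 11% to 15%; tripled: 36% to 47%;
- deaths up 7.5 or 14 points among delirious or comatose patients: 13% or 32%;
- deaths up 6.5 or 12.6 points through an equal added daily risk for everyone: 6% or 14%;
- delirium-to-coma rate doubled: up to 27%; tripled: up to 70%.

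One chain gave 18.9% and 54.0% for doubled and tripled death hazard. Its DCFD SD of 4.59 fits the planned 5.2 less well, and I do not rely on it.

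**The case against.** The strongest reply is that SO2 never stands alone. The primary outcome counts death and coma as bad, survival is SO1, and coma duration is pre-specified with the same tests. In one set of runs, trials with a favourable SO2 and no significant harm on 14-day mortality, coma duration or DCFDs were 2.4% for a doubled death hazard and 1.1% for a doubled coma rate, against 2.9% with no effect. With the doubled hazard, 14-day mortality alone was significant in 79% of trials.

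Much of this stands: a large harm would usually show somewhere. Three things limit it. DCFDs, the outcome a reader checks first, flagged a significant difference in under 10% of the false-favourable trials under a doubled death hazard. The SAP has no 14-day mortality test (SO1 is at 30 days, 90 days and 1 year), and coma duration is exploratory, offered to explain DCFDs, and itself shortened by death. No rule tells the reader to take SO2 together with the others.

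Other points stand in full. Delirium takes precedence over coma on mixed days, and the protocol has a hold rule for persistent oversedation; both soften the coma route. The protocol's mortality signal concerns long-term use outside the ICU, and section 2.3 itself says this trial differs.

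A reader might also infer that the SAP expressly scores early death as short delirium. It does not; the result follows from its silence together with the analysis set and the day count. Nor does it use worst rank as its main method for long-term outcomes: the main analysis there is inverse probability weighting, and the composite is a sensitivity analysis only.

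**Conclusion.** The point holds. Followed as written, the SAP lets early death and conversion of delirium to coma shorten SO2, and nothing in either document prevents it. The direction follows from the definitions; the size does not. For a death hazard doubled over 14 days, an otherwise null comparison would favour the drug in roughly one trial in seven to nine, with a shift of about 0.4 days (5.82 − 5.39 = 0.43). If deaths are few or balanced, the bias is small. The coma figures are too dependent on assumed rates to quote without their range.

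A reader might go further and conclude that a harmful drug could make the trial positive. The documents do not support that: the trial is judged on DCFDs, which count death and coma against the drug. The weakness is confined to a secondary outcome, and to the hypoactive, hyperactive and coma durations analysed the same way. It is still worth correcting, because the SAP presents its secondary comparisons as hypothesis-driven and tests them unadjusted.

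**What to change.** Before unblinding, amend SAP sections 6 to 8 as follows.

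1. State how death within the 14 days enters SO2.
2. Run the SO2 Kruskal-Wallis and proportional odds tests with those deaths ranked worst. This extends to a main analysis a device the SAP now uses only for long-term sensitivity. Keep raw delirium days as description.
3. Do the same for the hypoactive, hyperactive and coma durations.
4. Ranking death worst does not fully cure the coma route, so state that a shorter SO2 is not read as benefit on its own, but only alongside DCFDs, coma duration (with deaths ranked worst) and survival.

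The cost is one derived variable for each duration plus wording; no new data are needed. The downside is that the tested quantity becomes a ranked composite, closer to DCFDs and less easily stated in days. Reporting the raw days beside it keeps the component information.
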